2.2 Research status

Many literatures have reported risk factors for neurological complications in patients with MMD after revascularization,^{12, 27, 28} however, there is a lack of effective measures and clear criteria for how to reduce the incidence of neurological complications after revascularization in patients with MMD. A recent study reported the effect of combined remote ischemic treatment on neurological complications after STA-MCA anastomosis in patients with MMD.²⁹ This study demonstrated the potential of combined RIPC and RIPostC to reduce neurologic complications and the duration of hospitalization in patients undergoing STA-MCA anastomosis for MMD. However, since this study is a single-center study and only 108 patients were enrolled, the effectiveness of RIPC remains to be confirmed. In addition, the effect of direct revascularization varies greatly depending on the surgeon's experience and technique. When conducting a multicenter study, the results may be biased. At the same time, because this study enrolled MMD patients undergoing direct revascularization, it is

unclear whether RIPC can reduce the incidence of postoperative neurological complications in adults with ischemic MMD undergoing indirect revascularization. Whether RIPC is effective enough in adult ischemic MMD patients undergoing indirect revascularization to reduce postoperative neurological complications and improve prognosis? The current research quality is not sufficient to support clinical decision making. In adult ischemic MMD patients undergoing indirect revascularization, prospective clinical trials to confirm the clinical benefits and risks of RIPC procedure have become clinical problems that need to be addressed.

3. Primary Aim

- To evaluate the safety of remote ischemic preconditioning in adult ischemic MMD patients undergoing indirect revascularization
- To evaluate the clinical benefit of remote ischemic preconditioning in adults with ischemic MMD who underwent indirect revascularization

References

3. Kuriyama S, Kusaka Y, Fujimura M, Wakai K, Tamakoshi A, Hashimoto S, et al. Prevalence and clinicoepidemiological features of moyamoya disease in japan: Findings from a nationwide epidemiological survey.

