6.2 Exclusion Criteria

- Prior cerebral hemorrhage history
- Other brain or cerebrovascular disease
- Previous history of revascularization surgery
- Dependent (mRS > 2)
- Receive other type of revascularization surgery

- Peripheral blood vessel disease (especially subclavian arterial and upper limb artery stenosis or occlusion).
- Patients who do not agree with the study

7. Informed Consent

The principles of Informed Consent, according to FDA Regulations and ICH guidelines on GCP, will be followed. Investigator will submit a copy of the proposed consent form, together with the study protocol, to the central Institutional Review Board (IRB) at Beijing Tiantan Hospital for approval. Each eligible patient who wishes to participate in this study will be invited to give written informed consent. Before the consent is signed, a trained researcher will explain study purpose, description, duration, potential risks and anticipated benefits, cost and compensation, voluntary nature of participation, appropriate alternatives, treatment for study-related injury, whom to contact with questions or concerns or study-related injuries, maintenance of confidentiality of record, and funding source. Patients will be encouraged to consent for the blood drawing for biomarker testing only if they would be prepared to enroll in the trial.

8. Enrollment of Patients

All patients with moyamoya disease who visit the research center will be asked if they are involved in the study as long as they meet the inclusion criteria. This study is included in patients who have voluntarily participated in the study and signed

informed consent and did not meet the exclusion criteria.

9. Randomization of Patients

Patients was randomized by random number table

10. Image Data Evaluation

In this study, Suzuki staging was determined by DSA technique; subarachnoid hemorrhage, ischemic stroke (cerebral infarction), and cerebral hemorrhage were diagnosed using the Fourth National Conference on Cerebrovascular Diseases (1995).

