In order to prevent errors in the research due to the interpretation technique, this study set up a decision-making committee to uniformly judge the imaging data of the patients enrolled. Two experienced neuroimaging physicians conducted mutual blind interpretation, and the results of the inconsistent report should be ranked third. The senior neuroimaging chief physician will conduct a trial and finally submit true and reliable imaging results for all cases. The interpreter does not participate in the study design and does not know the patient's clinical information.

11. Bio sample test

Blood samples were drawn from the cubital vein; the points of measurement included baseline, pre-EDAS, right 1 hour and 24 hours post-EDAS. The collected blood samples were sent for examination, and plasma neuron specific enolase (NSE) and human S protein 100B (S-100B) levels were examined in the test samples.

11. Schedule of Follow-up and Post-study Follow-up Period

All patients will be followed up until the primary endpoint or the end of the trial.

Complete endpoint information will be obtained with the best effort irrespective of patient study status, unless patients withdraw consent to participate the trial. The face-to-face interview will be performed by study neurologists at discharge, at 6 months and at 12 months (or by telephone) after the recruitment of patients.

Visits	Windows	Definition
Randomization	0 day	Study Day 0 day
At discharge	0 day	Based on the number of hospitalization days
At 6 months	14 days	Day 166-194
At 12 months	30 days	Day 330-390

12. Quality Assurance

Periodic monitoring and auditing will be performed at each site to ensure that data generated during the study reflect what is specified in the protocol, and data consistence by comparing data in the case report form (CRF) and data collected in source documents for (CRF vs. source documents). If patients who have events go to non-study sites for treatment, source documents will be photocopied for review. It should be guaranteed that the study investigators and relevant study personnel are available during the monitoring visits and possible audits.

13. Statistical Consideration

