13.1 Sample size estimates

This study was a cohort study of prospective, multicenter, hospital-based, continuous enrollment patients. It is planned to choose three hospitals in Beijing. The investigation and registration of the ending events are carried out through hospital follow-up examinations, investigations, registration and hotline reports, face-to-face or telephone follow-up, and monitoring information database supplementation.

Sample size and power were calculated based on previous studies and postoperative neurological complications, which were much better to indicate the efficacy of RIPC.

We calculated the simple size and power with PASS, version 11 (NCSS, LLC, Kaysville, UT, USA). We expected $\approx 10\%$ of subjects in the RIPC group and 20% of subjects in the other 2 groups would have new postoperative neurological complications. The intended target sample size was 328 subjects allowing 15% loss to follow-up and with 90% power and an α of 0.05 (2-sided) of significance.

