13.2 Statistical Analyses

The results of the study were analyzed using IBM SPSS Statistics 23.0 (IBM Corp, Armonk, NY, USA) data analysis software. Charting was performed using GraphPad Prism 7.0a (GraphPad Software, La Jolla, CA, USA). Continuous variables obeying the normal distribution were expressed as mean \pm standard deviation, and two independent sample t-tests or paired t-tests were used for comparison between the two groups. Continuous variables with unknown distributions were expressed using median and interquartile range and compared between the two groups by Mann-Whitney U test or Wilcoxon rank sum test. The normality of the continuous variables

was tested using the Shapiro-Wilk W test. The categorical variables were expressed as frequency and percentage, and comparisons between the two groups were made using the Pearson chi-square test or the McNemar paired chi-square test. Correlation between the two variables was analyzed using Pearson, Kendall's tau-b or Spearman correlation coefficients according to the corresponding variable types. Prognostic information was analyzed by Kaplan-Meier survival analysis based on least squares method and compared between the two groups using log-rank test. All statistical tests were two-sided, and the results were considered statistically significant at $P < 0.05$.

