13.3 Clinical Site Effect

All revascularization surgeries will be performed by experienced neurosurgeon.

14. Data Safety Monitoring Committee

A Data Safety Monitoring Board (DSMB) is composed of Academic Members, including an independent statistician, who are not otherwise participating in the trial. A DSMB charter including membership role and responsibilities will be approved by both the DSMB and the Executive Committee before the start of the trial. DSMB will meet approximately every three months to review the progress of this study (e.g. enrollment, site performance, meeting risk factor targets) as well as data on the safety of both treatment arms (e.g., side effects of RIPC) to ensure that the study meets the highest standards of ethics and patient safety. Using guidelines established by the committee and the principal investigators before the study begins, the DSMB may

recommend termination of the study if one treatment arm is found to be unequivocally more efficacious than the other or if one of the treatment arms is found to be unsafe.

Additionally, the DSMB may recommend modifications to the protocol if a reversible safety issue is identified. A letter including written recommendations and their rationale will be provided to the Chairs of the Steering Committee immediately after each DSMB meeting. This letter will be provided to the central IRBs at their request.

Committee member: [name], [name], [name]

15. Institutional Review Board/Independent Ethics Committee(IRB/IEC)

The Investigator or the Sponsor must submit this Clinical Trial Protocol to the central IRB located at Beijing Tiantan Hospital, and is required to forward to the Sponsor a copy of the written and dated approval/favorable opinion signed by the Chairman with Ethics Committee (IRB/IEC) composition.

The following information should be clearly stated on the written approval/favorable opinion: The Clinical Trial information (study number, Clinical Trial Protocol title and version number), the documents reviewed (Protocol, Informed Consent Form, Investigator's Brochure, etc.), the list of voting members along with their qualification and the date of the review.

Investigational Product will not be released at the study site and the Clinical Trial will not be initiated until a copy of this written and dated approval/favorable opinion has been received by the Sponsor.

During the Clinical Trial, any amendment or modification to the Clinical Trial

[figure not shown]

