Protocol should be submitted to the Ethics Committee (IRB/IEC). It should also be informed of any event likely to affect the safety of patients or the continued conduct of the Clinical Trial, in particular any change in safety. All updates to the Investigator's Brochure will be sent to the Ethics Committee (IRB/IEC). If requested, a progress report will be sent to the Ethics Committee (IRB/IEC) annually and a summary of the Clinical Trial's outcome at the end of the Clinical Trial.

16. Safety Outcomes Assessment

The following adverse events were defined as safety outcomes: (1) elevation of plasma NSE and S-100B levels beyond normal limits after RIPC and sham RIPC procedure; (2) inability to tolerate RIPC or sham RIPC procedure that leads to the discontinuation from the study; (3) objective signs of tissue or neurovascular injury resulting from RIPC and sham RIPC procedure. An inspection that was done by staffs blinded to the study protocol included palpation of distal radial pulses, visual inspection for local edema, erythema and skin lesions, and palpation for tenderness. These safety outcomes were evaluated by observers blinded to the treatment assignment, and any suspicious adverse event associated with RIPC or sham RIPC procedure was reported to the investigators.

APPENDIXS

Study Flow Chart

Schedule of Visits and Test

	Visit 1	Visit 2	Visit 3	Visit 4	Event visit
Assessments	Screening/Randomize	At discharge	At 1 year ± 1 month	Every 12 months ±1 month	
Informed Consent	✓				
Eligibility criteria	✓				
Patient Randomization	✓				
Relevant medical history	✓				
Demographics	✓				
MRI before Surgery	✓				
CTP before Surgery	✓				
DSA before Surgery					
Vital signs	✓				✓
Modified Rankin Score	✓	✓	✓	✓	✓
MRI after surgery		✓	✓	✓	
CTP after surgery		✓	✓	✓	✓
DSA after surgery		✓	✓		✓
Current Medications	✓	✓	✓	✓	✓
Endpoints		✓	✓	✓	✓

modified Rankin Scale

The modified Rankin Scale (mRS) is a scale commonly used for measuring the degree of disability or dependence in the daily activities of individuals who have suffered a stroke, and it has become the most widely used clinical outcome measure for stroke clinical trials.

Description	Score (select one)
No symptoms at all	0 
No significant disability despite symptoms; able to carry out all usual duties and activities	1 

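### Optional improvement: where CTP perfusion or NSE/S-100B is compared between arms as a continuous value, adjust for the baseline value already collected; keep the chi-square as primary for the binary 30-day endpoints

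*Combined protocol and SAP*

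**What the plan says.** Section 13.2 gives a general list of tests. Continuous variables are compared by t-test if normally distributed and otherwise by Mann-Whitney or rank sum test. For categorical variables, "comparisons between the two groups were made using the Pearson chi-square test or the McNemar paired chi-square test". Time-to-event data are compared by log-rank test. No regression model, covariate or stratum appears.

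Baseline values of two continuous measures are nevertheless planned. The Schedule of Visits and Test in the appendix places pre-operative CTP at Visit 1, with CTP repeated at discharge and at later visits. The Bio sample test section lists NSE and S-100B at baseline, before EDAS, and 1 and 24 hours after it.

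The Visit 1 column also holds "Modified Rankin Score" and "Relevant medical history". Section 13.1 says "It is planned to choose three hospitals in Beijing", and section 9 randomises by random number table with no stratification stated. Section 13.3, Clinical Site Effect, consists of one sentence: "All revascularization surgeries will be performed by experienced neurosurgeon".

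**The concern.** When an outcome is measured before and after randomisation, part of the spread in the follow-up value is already explained by the baseline value. A two-sample test on follow-up values leaves that part in the error term. A test on change scores removes it with a fixed weight that is usually not the best one. ANCOVA estimates the weight from the data. At stake is the width of the confidence interval for perfusion and the blood markers. The validity of the comparison is not in question.

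There is also a trap in the blood sampling. Two draws precede surgery, and only one of them is a true baseline. Adjusting for the other could remove part of the treatment effect.

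**Working it through.** **Inputs.** The plan gives no figure for the precision of any continuous outcome, so there is none to reproduce. It also gives no correlation between baseline and follow-up. I assume r = 0.3, 0.5 and 0.7, and equal variances at the two times.

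**Variance of the arm difference**, relative to comparing follow-up values:

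- follow-up values: 1
- change scores: 2(1 - r)
- ANCOVA: 1 - r²
- ANCOVA against change scores: (1 - r²) / [2(1 - r)] = (1 + r)/2

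| r | ANCOVA vs follow-up values | Variance cut | ANCOVA vs change scores | Variance cut |
|---|---|---|---|---|
| 0.3 | 1 - 0.09 = 0.91 | 9% | 1.3/2 = 0.65 | 35% |
| 0.5 | 1 - 0.25 = 0.75 | 25% | 1.5/2 = 0.75 | 25% |
| 0.7 | 1 - 0.49 = 0.51 | 49% | 1.7/2 = 0.85 | 15% |

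Confidence-interval width changes by the square root. Against follow-up values it falls by about 5, 13 and 29%; against change scores, by about 19, 13 and 8%. These figures concern a comparison of means and do not carry over directly to Mann-Whitney.

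**Cost in degrees of freedom.** With 328 patients less 15%, about 278 are evaluable. Error degrees of freedom go from 276 to 275, a factor of 276/275 = 1.004 in the residual variance.

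**Which blood draw.** Section 4 places conditioning, real or sham, on at least five days before EDAS. The Bio sample test section lists baseline and pre-EDAS as separate time points. The pre-EDAS draw therefore follows conditioning and may already carry its effect. CTP at Visit 1 belongs to the screening and randomisation visit, so it precedes conditioning.

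**Binary 30-day endpoints.** Section 13.1 states 328 patients for 20% versus 10%, 90% power, two-sided 0.05 and 15% loss. The two-proportion formula gives 266 per arm, 532 in total and 532/0.85 = 626 after loss, so 328 is not reproduced. Power from the same formula is 64.7% at 278 evaluable and 72.0% at 328. That shortfall is a separate matter.

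Logistic adjustment was simulated at 278 evaluable (5,000 trials per row) with three hospitals and three baseline covariates of assumed strength. Changes in power are in percentage points against chi-square:

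| c-statistic (assumed) | Wald test | Likelihood ratio test |
|---|---|---|
| 0.50 | -0.9 | +0.1 |
| 0.61 | -0.6 | +0.7 |
| 0.66-0.68 | +1.0 to +1.3 | +2.3 to +2.5 |
| 0.72 | +2.2 | +3.6 |
| 0.75 | +4.4 | +5.8 |
| 0.80 | +7.6 | +8.8 |

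A second simulation (100,000 trials per scenario) used hospital, onset type and baseline mRS, with a standard error that held the 5% level. It gave:

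- covariates not prognostic: -0.8
- odds ratios of 2 for onset type and 1.5 per mRS point: 0.0
- odds ratios of 3 and 2: +1.3
- odds ratios of 3 and 2, plus hospital risks of 10/20/30%: +2.8

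Expected events are 139 × 0.20 + 139 × 0.10 = 41.7. Over five coefficients (arm, two for hospital, onset type, mRS) that is about 8 each.

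**The case against.** **Against the point itself.** Nothing in 13.2 is wrong, and the improvement concerns an analysis that the plan barely specifies. Section 5.2 gives perfusion status no scale, and section 16 defines the blood-marker safety outcome as a level beyond normal limits, which is binary. The paired tests named in 13.2 may be meant for before-and-after values, so baseline data may not be wholly unused. Blood sampling also rests on consent ("Patients will be encouraged to consent for the blood drawing for biomarker testing") and has no row in the visit schedule, so baseline samples may be incomplete. All of this stands, and it makes the recommendation conditional on a continuous comparison being made. It does not remove the recommendation. A paired test within an arm does not compare the arms, and ANCOVA is at least as precise as comparing follow-up values or change scores, apart from the one degree of freedom.

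**Stronger readings that a reader might infer.**

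- *The unadjusted chi-square is a flaw and should give way to an adjusted primary analysis.* The documents do not support this. Randomisation is unstratified, so the chi-square is valid. Section 2.2 says that risk factors have been reported but gives no strengths, and nothing shows that hospital, onset type or baseline mRS predicts 30-day events. Baseline mRS can only be 0 to 2, because section 6.2 excludes higher scores.
- *Section 13.3 owes the reader a site model.* Its heading might suggest so, but the text handles site by design through experienced surgeons, and section 10 adds central image reading ("Two experienced neuroimaging physicians conducted mutual blind interpretation"). Section 2.2 says "the effect of direct revascularization varies greatly depending on" who operates; that remark is about direct surgery, not the indirect procedure studied here.
- *Adjustment would repair the power.* A change of about -1 to +3 points on 65 to 72% does not approach the stated 90%.

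**Conclusion.** This is an optional, low-cost improvement and not an error. Where CTP perfusion measures or NSE/S-100B levels are compared between arms as continuous values, ANCOVA on the baseline of the same measure would reduce variance by 9 to 49% against follow-up values, or by 35 to 15% against change scores, as r runs from 0.3 to 0.7. The 49% figure should not be quoted alone. It needs r = 0.7 and a plan that compares follow-up values, and neither is established.

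For the binary 30-day endpoints the planned chi-square should remain primary. The range of about -1 to +3 points for a logistic model holds for assumed covariates of none to moderate strength (c-statistic up to about 0.70). It is not an upper bound, because stronger covariates give more, and no power gain should be claimed.

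**What to change.** **In section 13.2:**

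1. Where CTP perfusion or NSE/S-100B is compared between arms as a continuous value, prespecify ANCOVA with the baseline value of the same measure as covariate. Name the perfusion measure and the scale of analysis (raw or log) in advance, since 13.2 otherwise falls back on Mann-Whitney for non-normal data.
2. For blood markers, use the baseline draw, defined as taken before the first conditioning session. Do not use the pre-EDAS draw as a covariate.
3. State how patients without a baseline sample are handled, for example by filling in the overall baseline mean with a missing indicator, so that patients with a follow-up value are not dropped.
4. Keep the chi-square as primary for both binary 30-day endpoints. If wanted, add one prespecified logistic model with arm, hospital, onset type and baseline mRS, labelled as a sensitivity analysis. It is practical mainly for cerebrovascular events. For death or dependency at assumed rates of 5% versus 2.5% (about 10 events), the full list gave separation in 24 to 26% of simulated trials.

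**Cost:** SAP wording, one degree of freedom, a little more analysis work and the missing-baseline rule. No new patients or data are needed.

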Effects of **R**emote **I**schemic Pre-Conditioning on Neurologic
Complications in Adult Ischemic **M**oyamoya Disease Patients
Undergoing **E**ncephaloduroarteriosynangiosis (**RIME**)

—— A Prospective, Multi-center, Randomized Controlled Trial ——

Study Protocol

Neurosurgical Principal Investigator

[name]

Professor of Neurosurgery

Beijing Tiantan Hospital, Capital Medical University, Beijing

Peking University International Hospital, Peking University, Beijing

[name]

Professor of Neurosurgery

Beijing Tiantan Hospital, Capital Medical University, Beijing

Peking University International Hospital, Peking University, Beijing

[name]

Professor of Neurosurgery

Beijing Tiantan Hospital, Capital Medical University, Beijing

Peking University International Hospital, Peking University, Beijing

August 20, 2019

1. Protocol Synopsis

Title	Effects of Remote Ischemic Pre-Conditioning on Neurologic Complications in Adult Ischemic Moyamoya Disease Patients Undergoing Encephaloduroarteriosynangiosis
Acronym	RIME
Objectives	
• To evaluate the safety of remote ischemic preconditioning in adult ischemic MMD patients undergoing indirect revascularization;• To evaluate the clinical benefit of remote ischemic preconditioning in adults with ischemic MMD who underwent indirect revascularization.
Study Design	
This study was a multi-center, prospective, randomized, controlled trial of randomized (1:1) adult ischemic MMD patients undergoing indirect revascularization into two groups:
 
1. RIPC group Remote limb ischemic preconditioning (RIPC) is consisted of five 5-min cycles of bilateral arm ischemia/reperfusion, it is induced by a sphygmomanometer placed on bilateral arm and inflated to 200 mmHg for 5-min followed by deflating the cuff for 5-min, patients in the RIPC group will do it twice a day for at least five days before EDAS.2. sham RIPC group Sham RIPC group is consisted of five 5-min cycles of bilateral arm ischemia/reperfusion, induced by a sphygmomanometer placed on bilateral arm and inflated to 60 mmHg for 5-min followed by deflating the cuff for 5-min, they will do it twice a day for at least five

	days before EDAS.
Primary endpoint	
 • All cerebrovascular events (ischemic stroke, cerebral hemorrhage, transient neurological deficits) within 30 days post-surgery • All death or dependent (mRS > 2) within 30 days post-surgery

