2.1 Background

Moyamoya disease (MDD) is a chronic ischemic cerebrovascular disease characterized by chronic progressive stenosis of the bilateral internal carotid artery.¹ Chronic progression of the disease can lead to the formation of abnormal vascular networks, including vascular network compensation for the formation of the skull base and the initial pathological changes in the area of cerebral infarction.² MMD is common among East Asians, including Japan, South Korea and China.³⁻⁵ The clinical manifestations of MMD are mainly divided into two types in the Asian population: ischemic and hemorrhagic. The ischemic type accounts for about 70%, and the

hemorrhagic type accounts for about 30%.^{6,7}

For the treatment of patients with MMD, the main purpose is to prevent further stroke events and reduce the rate of recurrent stroke.⁸ There are two types of treatment for patients with MMD: surgery and conservative treatment.⁹ Surgical treatment includes direct revascularization and indirect revascularization. Surgical treatment has been widely recognized for reducing ischemic MMD re-stroke, but there is still controversy about hemorrhagic MMD.^{10,11} Indirect revascularization is a simpler, less laborious technique than direct revascularization requiring manual anastomosis of extracranial donor vessels and intracranial recipient vessels, with a lower risk of postoperative complications.^{12,13} Furthermore, many recent studies demonstrated that the long-term efficacy of indirect revascularization has no significant difference with direct revascularization.¹³⁻¹⁵ However, due to insufficient blood supply to the brain in patients with MMD, the vascular reactivity of the cerebral vessels is decreased,¹⁶ leading to poor tolerance to hemodynamic changes.¹⁷ Cerebral hypoperfusion may occur after indirect revascularization surgery, leading to postoperative ischemic events and postoperative neurological deterioration,¹² which may increase postoperative morbidity and mortality. Therefore, patients undergoing cerebral revascularization require an effective neuroprotective strategy.

Several animal and human studies have shown that non-fatal ischemic injury has an overall protective effect on pretreated tissues and other distal organs, which is called distal ischemic preconditioning (RIPC).^{18,19} RIPC has cardioprotective effects on patients undergoing cardiac surgery.²⁰ In terms of neuroprotection, RIPC reduces

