5.1 Primary Endpoint

- All cerebrovascular events (ischemic stroke, cerebral hemorrhage, transient neurological dysfunction) within 30 days post-surgery
- All death or dependent (mRS > 2) within 30 days post-surgery

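### Two 30-day primary endpoints have no success rule; if a win on either counts, the false-positive rate exceeds the 5% used for sizing

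*Combined protocol and SAP*

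**What the plan says.** Section 1 (synopsis) and section 5.1 each place two bullets under one primary-endpoint heading. In the synopsis the first is "All cerebrovascular events (ischemic stroke, cerebral hemorrhage, transient neurological deficits) within 30 days post-surgery". In section 5.1 the second is "All death or dependent (mRS > 2) within 30 days post-surgery".

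Section 13.2 chooses tests by variable type, with Pearson chi-square for between-group comparisons of categorical variables, and closes with "All statistical tests were two-sided, and the results were considered statistically significant at" P < 0.05. It gives no testing order, composite, both-required rule or split of alpha.

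Section 13.1 sizes the trial on one outcome: "Sample size and power were calculated based on previous studies and postoperative neurological complications, which were much better to indicate the efficacy of RIPC". It expects about 10% in the RIPC group and "20% of subjects in the other 2 groups would have new postoperative neurological complications", "with 90% power and an α of 0.05 (2-sided) of significance". It does not call that outcome the sole or lead primary endpoint, and its label matches neither bullet exactly.

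**The concern.** With two primary endpoints and every test judged at 0.05, the plan does not say what makes the trial positive. A report could miss on cerebrovascular events and still claim a primary-endpoint success on death/dependency, or the reverse. If that is allowed, the chance of a false claim is no longer the 5% assumed for sizing.

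A composite or a both-required rule would not inflate the error. But section 13.1 gives no rates for either definition, so the power would be unknown. The choice of rule can decide the trial's conclusion, and it is credible only if fixed before the results are seen.

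**Working it through.** **Inputs from the documents.** Two binary 30-day endpoints (sections 1 and 5.1); Pearson chi-square at two-sided 0.05 (13.2); 10% vs 20%, 328 patients, 15% loss, 90% power (13.1); 1:1 allocation (section 4). Per arm: 328/2 = 164 with no loss, and 328 × 0.85/2 ≈ 139 after loss.

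**Inputs assumed.** Under the null, events at 10% to 20% in both arms; death/dependency at 0.5% to 15%; death/dependency arising only after an event (nested), or half of it outside events. The documents give no death/dependency rate and no overlap.

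**The plan's own figure.** n per arm = [1.96·√(2·0.15·0.85) + 1.2816·√(0.2·0.8 + 0.1·0.9)]² / 0.10² = (0.990 + 0.641)²/0.01 ≈ 266. The total is 532, and 532/0.85 ≈ 626. The stated 328 is not reproduced; it gives about 65% power at 139 per arm and 72% at 164. This is a separate issue. The error rate below depends on sample size only through the discreteness of the test.

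**Either-endpoint rule, limits.** Independent endpoints: 1 − 0.95² = 0.0975. Identical endpoints: 0.05.

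**Nested endpoints, approximation.** With event rate p₁ and death/dependency rate p₂, the correlation of the two test statistics is ρ = √[p₂(1 − p₁) / (p₁(1 − p₂))].
- p₁ = 20%, p₂ = 5%: ρ = √(0.04/0.19) = 0.46, and the bivariate normal gives 9.2%.
- p₁ = 10%, p₂ = 7.5%: ρ = √(0.0675/0.0925) = 0.85, giving 7.4%.
- p₁ = 10%, p₂ = 9%: ρ = √(0.081/0.091) = 0.94, giving about 6.6%.

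**Nested endpoints, simulated** (Pearson without continuity correction, at least 300,000 null trials per setting; probability that either test rejects, two-sided):

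| Events | Death/dependency | 139 per arm | 164 per arm |
|---|---|---|---|
| 10% | 0.5% | 5.3% | 5.9% |
| 10% | 1% | 7.2% | 8.1% |
| 10% | 5% | 8.1% | 8.4% |
| 10% | 7.5% | 7.1% | 7.5% |
| 10% | 9% | 6.2–6.4% | 6.6–6.7% |
| 20% | 5% | 9.0% | 9.0% |
| 20% | 15% | 7.5% | 7.5% |

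Across event rates, death/dependency of 0.5% gives 5.3% to 6.0%.

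**Half of death/dependency outside events**, rates 2.5% to 10%: 8.9% to 9.7%.

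**Only results favouring RIPC.** The simulated settings give 2.7% to 4.9%, with a limit of 2.5% when the endpoints coincide. The single-endpoint base is 2.5%.

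**Sensitivity to the test.** At 1% death/dependency, about 139 × 0.01 = 1.4 to 164 × 0.01 = 1.6 patients per arm are expected. With Fisher's exact test for death/dependency only, the nested settings at 1% to 10% run from about 5% to 7% two-sided, and the 1% settings sit at about 5%.

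**Both-required rule, power with events 10% vs 20%** (139 / 164 per arm):

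| Death/dependency | Nested | Half outside events |
|---|---|---|
| 1% vs 2% | 6.9% / 8.5% | 6.1% / 7.7% |
| 2.5% vs 5% | 15.7% / 19.5% | 13.5% / 17.3% |
| 5% vs 10% | 31.2% / 38.0% | 26.2% / 32.9% |

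**Events first, then death/dependency only if events are significant.** Under the null the error is that of the events test alone: 4.8% to 5.1% in the simulations.

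**The case against.** The strongest reply is that the plan does point to one endpoint. Section 13.1 sizes on neurological complications and says why they are preferred, the endpoint headings are singular, and the follow-up section also refers to the primary endpoint in the singular. On that view events lead, or the two bullets form one composite, and the error is not inflated. This has weight: the inflation depends on how the plan is read, and the certain defect is the missing rule. But a sizing rationale is not a decision rule, and a singular heading over two bullets fits a composite, co-primaries or two separate endpoints equally well.

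A reader might infer that the false-positive rate is 9.75%. The documents do not support that figure, which needs independent endpoints. Section 6.2 excludes patients already dependent at entry, and a disabling stroke within 30 days counts in both endpoints, so positive correlation is likely.

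A reader might also infer that 7% is a floor whenever death/dependency is at least 1%. It is not: the rate drops again as death/dependency approaches the event rate. Very low rates are plausible too, since section 2.1 describes indirect surgery as carrying fewer problems, "with a lower risk of postoperative complications", and there the inflation is small and depends on the test used.

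The two-sided figures also count results favouring sham. For a false claim of RIPC benefit, the directional figures are the relevant ones. Nor does section 13.2 leave the endpoints without any test: Pearson chi-square applies to both. What is missing is how the two results combine.

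**Conclusion.** The omission is certain from the text: two primary endpoints, one blanket threshold, no rule for success. If either endpoint may carry the claim, the error exceeds the 5% used for sizing. Under the assumed rates and the uncorrected Pearson test, with death/dependency arising only after an event, the two-sided rate is about 7% to 9% for death/dependency from 1% up to about three quarters of the event rate. It is 5.3% to 6.0% at 0.5%, and 6.2% to 6.7% at 9% with events at 10%. It reaches at most 9.7% if half of death/dependency falls outside events. Counting only RIPC-favouring results, the total is about 2.5% to 4.9% against 2.5%.

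A composite or both-required reading removes the inflation but leaves the power unstated; a both-required rule would have about 6% to 38% under the assumed effects. Confidence is high in the omission and only moderate in the size. It should be fixed.

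**What to change.** Before unblinding, write one rule into sections 1, 5.1 and 13.2. Recommended: test 30-day cerebrovascular events first at two-sided 0.05, and test 30-day death or mRS > 2 at two-sided 0.05 only if the first test is significant. Events go first because they are the closest match to the outcome used for sizing.

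In section 13.1 the sponsor should confirm which endpoint the 10% and 20% describe. The documents attach them only to postoperative neurological complications from previous studies, so they should not simply be relabelled. If a composite or co-primaries were intended, say so and restate the power for that definition.

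The cost is about three sentences, with no extra patients or visits, and events keep the full 0.05. The downside is that a win on death/dependency alone would no longer be confirmatory.

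The sequence controls error for a single final analysis only. The efficacy looks that section 14 leaves open to the DSMB, and the power of 328 patients, are separate issues. So is the visit schedule, which lists no 30-day visit at which mRS would be recorded.
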